3.2. Study Endpoints

3.2.1. Effectiveness Endpoints

The primary effectiveness endpoint will be change in Schirmer score from baseline. Secondary effectiveness endpoints include changes in Ocular Surface Disease Index (OSDI) score, corneal staining score, tear break-up time and tear meniscus height

3.2.2. Safety Endpoints

The primary safety endpoint will be the proportion of participants that experience one or more device-related adverse events (e.g., irritation, conjunctival injection, epiphora, subconjunctival hemorrhage, canaliculitis, punctal stenosis, eyelid telangiectasia, eyelid edema, eyelid induration, eyelid erythema).

3.3. Study Population

The study will enroll up to 13 participants at one site that provide informed consent and meet the eligibility criteria below.

3.3.1. Inclusion Criteria

To be eligible for the study, potential participants must meet all of the following inclusion criteria at the Screening Visit:

- Twenty-one (21) to 80 years of age
- Baseline OSDI score of at least 13 with no more than 3 responses of “not applicable”
- In both eyes, a baseline Schirmer test with anesthetic of \leq 10 mm/5 minutes
- Literate, able to speak English and able to complete the questionnaire independently
- Willing to sign the informed consent and deemed capable of complying with the requirements of the study protocol.

3.3.2. Exclusion Criteria

To be eligible for the study, potential participants must not meet any of the following exclusion criteria:

- Use of ophthalmic cyclosporine or lifitegrast within 30 days prior to Day 0
- History of surgical punctal occlusion (e.g., cauterity), canalicular infection or canalicular surgery
- Corneal transplant in either eye
- Ocular surgery (such as cataract surgery or LASIK) in either eye within six months of the Baseline Visit
- A systemic condition or disease not stabilized or judged by the investigator to be incompatible with participation in the study (e.g. current systemic infection, uncontrolled autoimmune disease, uncontrolled immunodeficiency disease)
- The history or presence of any ocular disorder or condition in either eye that, in the opinion of the investigator, would interfere with the interpretation of the study results (e.g., significant corneal or conjunctival scarring, pterygium or nodular pinguecula; current ocular infection (except mild blepharitis), conjunctivitis or inflammation not associated with dry eye; anterior (epithelial) basement membrane corneal dystrophy or other clinically significant corneal dystrophy or degeneration; history of ocular herpetic infection; evidence of keratoconus; lid or lacrimal cancer.
- Active severe systemic allergy, seasonal allergies, rhinitis or sinusitis requiring treatment (i.e. antihistamines, decongestants, oral or aerosol steroids)
- Use of steroids, including administration by systemic, inhaled or topical ocular routes (dermatologic steroids not applied to the eyelids are allowed)
- Participation in a clinical trial during the past 30 days
- Women who are pregnant, planning a pregnancy, or nursing at study entry.

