3. STUDY DESIGN

3.1. Description of Study Design

The study is a single-arm, single-center, randomized, single-masked prospective study to evaluate Restylane-Defyne for canalicular occlusion in participants with mild to moderate dry eye disease.

Each participant will have a Screening Visit to determine eligibility. Prior to performing any testing specifically for the Screening Visit, participants will be provided with an IRB approved informed consent form and be given the chance to review and ask questions before written informed consent is obtained. The Screening Visit should occur within 30 days prior to application of the HA gel on Study Day 0 and may occur on Day 0. Participants that meet all eligibility criteria will be invited to participate in the study.

Participants that return or are present for Study Day 0 will be enrolled in the study and will receive the device. Participants will be followed for 42 days and will be seen for follow-up exams at 3, 14 and 42 days.

Participants may continue to use their artificial tears. The use of artificial tears will be recorded.

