3.8.1. Screening (Day -30 to 0)

Any tests or procedures that are performed to confirm eligibility and are not standard of care must be performed AFTER the potential participant has signed the Informed Consent Form.

The following procedures are performed at the Screening visit:

- Obtain medical history and confirm potential participant's age
- Obtain written informed consent
- Perform urine pregnancy test for women of childbearing age
- Have potential participant complete the Ocular Surface Disease Index (OSDI) for each eye individually
- Perform Corrected Distance Visual Acuity
- Perform baseline TBUT test
- Perform baseline tear meniscus height test
- Administer fluorescein stain
- Perform slit-lamp biomicroscopy and assess corneal staining using the NEI grid and scoring system
- Perform baseline Schirmer test with topical anesthetic

If at any point in this process, the potential participant fails to meet eligibility, the process should be discontinued, and the potential participant should be recorded as a screen failure along with the reason.

3.8.2. Day 0

The following procedures are performed at the Day 0 visit:

- Have participant complete the OSDI for each eye individually
- Perform Corrected Distance Visual Acuity
- Instill HA device in inferior canaliculus of eye randomized to the device
- Instill saline in inferior canaliculus of fellow eye

3.8.3. Day 3 and 14

The following procedures are performed at the intermediate follow-up visits, Days 3 and 14:

- Have participant complete the OSDI for each eye individually
- Perform corrected distance visual acuity
- Perform slit-lamp biomicroscopy

3.8.4. Day 42

The following procedures are performed at the Day 30 visit:

- Have participant complete the Ocular Surface Disease Index (OSDI) for each eye individually
- Perform Corrected Distance Visual Acuity
- Perform TBUT test
- Perform tear meniscus height test
- Administer fluorescein stain
- Perform slit-lamp biomicroscopy and assess corneal staining using the NEI grid and scoring system
- Perform Schirmer test with topical anesthetic
- Remove device from inferior canaliculus by irrigation (if necessary for complete removal, hyaluronidase may be used)

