3.9. Concomitant Medications and Therapies

All concomitant medications used within the 30 days prior to the screening visit, including medications used for relief of dry eye symptoms, will be documented on the case report form. Any initiation of new medications or changes to current medications during the course of the study should be recorded on the appropriate case report form. No other experimental drug or device should be used within 30 days prior to the Screening Visit or during the course of the clinical trial.

At the end of the Screening Visit, participants should be instructed not to use perfume or make-up on study days. Participants should also be instructed to refrain from administration of any chronic ophthalmic medication for two hours before their visit.

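### The cyclosporine/lifitegrast exclusion period is counted back from Day 0, but the baseline tear tests it should protect are taken at Screening, up to 30 days earlier

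*Protocol*

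**What the plan says.** Section 3.3.2, like the synopsis, excludes "Use of ophthalmic cyclosporine or lifitegrast within 30 days prior to Day 0". Section 3.1 sets the timing of Screening: "The Screening Visit should occur within 30 days prior to application of the HA gel on Study Day 0 and may occur on Day 0".

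Section 3.8.1 places the baseline tear tests at Screening: "Perform baseline Schirmer test with topical anesthetic", "Perform baseline TBUT test" and "Perform baseline tear meniscus height test", together with corneal staining. Section 3.8.2 lists OSDI and visual acuity at Day 0, and Appendix A adds a slit-lamp examination. Neither repeats Schirmer, staining, break-up time or meniscus height on that day. Those four measures are next taken at Day 42 ± 5.

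Section 3.2.1 makes the Schirmer change from baseline the primary effectiveness endpoint. Section 4.6 judges effectiveness by comparing the change to 6 weeks in the device eye with that in the sham eye.

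Other look-backs use a different anchor. The ocular surgery criterion in section 3.3.2 counts from the Baseline Visit. Section 3.9 documents "All concomitant medications used within the 30 days prior to the screening visit" and applies its bar on other experimental products from that same visit. Appendix A marks eligibility only in the Baseline column.

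**The concern.** An exclusion period for prior therapy is useful to a change-from-baseline endpoint only if it ends at or before the baseline measurement. Here it ends at instillation, when none of the four tear measures is taken. A participant can meet the criterion in full and still have had little or no drug-free time when the baseline Schirmer was recorded.

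Two things are at stake. The first is the within-eye change in Schirmer, the form in which section 3.2.1 words the primary endpoint: it could contain a change due to stopping the drug as well as one due to the device. The second is the set of entry values, Schirmer of at most 10 mm in 5 minutes and OSDI of at least 13, which may be judged soon after the last dose. If the clean baseline was never measured, no later analysis can recover it.

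**Working it through.** **Inputs.** Exclusion period: 30 days back from Day 0 (section 3.3.2). Screening: Day -s, with s from 0 to 30 (sections 3.1 and 3.8.1). Final tear tests: Day 42 ± 5, that is Day 37 to Day 47 (Appendix A). Goal of 10 completers (synopsis).

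**The plan's own figure.** Section 3.4 gives up to 72 days in the study. The 30-day screening window plus 42 days of follow-up is 30 + 42 = 72, so the figure reproduces. It is also the longest nominal interval from baseline to the final Schirmer test.

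**Guaranteed drug-free time at baseline.** If the last permitted use is 30 days before Day 0 and Screening is on Day -s, the minimum is 30 - s days. If use on Day -30 itself counts as inside the excluded period, the last permitted use is Day -31 and the minimum is 31 - s.

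| Screening day | Minimum, 30 - s | Minimum, 31 - s |
|---|---|---|
| Day 0 | 30 | 31 |
| Day -7 | 23 | 24 |
| Day -14 | 16 | 17 |
| Day -21 | 9 | 10 |
| Day -30 | 0 | 1 |

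**Guaranteed drug-free time at the final visit, if the drug is not resumed.** 30 + 42 = 72 days nominally. Over the visit window it runs from 30 + 37 = 67 to 30 + 47 = 77 days. Under the second reading each figure is one day longer.

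**After reconciliation.**
- Same period counted back from Screening, with Screening on Day -30: at least 30 days at baseline, 30 + 30 = 60 at Day 0, and 60 + 42 = 102 at Day 42.
- Tear tests taken on Day 0 before instillation: at least 30 days at baseline and 72 at Day 42.

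Either way, every baseline value has the 30 days that the protocol itself chose, whatever the screening day.

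**Weight of one case.** One affected participant among 10 completers is 1/10 = 10% of the analysed participants. This is a count and does not measure bias.

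**The case against.** The strongest reply is that the main comparison hardly suffers. A reader might infer that the mismatch biases the device-versus-sham contrast, especially if drops were used in one eye only. The documents do not support that. Sections 3.6 and 4.3 assign the device eye by a randomization sequence, so a previously treated eye is as likely to receive the device as the sham. Unequal use therefore adds noise and chance imbalance in a small sample, not systematic bias. Where both eyes were treated, a withdrawal effect largely cancels in the within-person comparison of section 4.6. This part of the reply stands.

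It is also fair to say that near-zero drug-free time needs Screening close to Day -30 and a last dose just before it, and that Screening on Day 0 gives the full 30 days. However, the shortfall is graded: every day between Screening and Day 0 removes one guaranteed day. Separate visits are also the usual flow in section 3.5, where eligible participants are scheduled to return for Day 0.

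Three further points limit the weight. The study is a pilot with no clinical hypothesis and no sample size calculation (sections 4.1 and 4.2). The medication history in section 3.9 would make recent users identifiable. Someone who meets the Schirmer and OSDI thresholds soon after the last dose has still met them, so the harm to eligibility is modest. None of these supplies a clean baseline for the within-eye change.

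**Conclusion.** The mismatch is real and follows from the text alone. Guaranteed drug-free time at baseline is about 30 - s days, down to 0 to 1 day at the edge of the screening window, against at least 67 to 77 days at the final visit. It affects the within-eye change from baseline and the entry values. It leaves the randomized between-eye comparison largely intact, so this is worth correcting but does not undermine the study.

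The conclusion assumes that some participants stopped one of these drugs shortly before Screening and did not resume it. The second condition is not guaranteed: section 3.9 requires medication changes to be recorded but does not expressly bar these drugs during follow-up. The protocol gives neither the size nor the duration of a withdrawal effect on Schirmer, so neither a bias figure nor its direction can be stated.

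Two further inferences should not be drawn:
- That the site cannot apply the criterion because eligibility is marked only at Baseline. The site schedules Day 0, enrollment occurs on that day, and a known last-dose date lets the site plan for it. What is missing is a scheduled confirmation.
- That the steroid exclusion is faulty for lack of a look-back. Its wording, "Use of steroids, including administration by systemic, inhaled or topical ocular routes", reads naturally as current use and has no bearing on the Day 0 anchor.

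**What to change.** Reconcile section 3.3.2 and the synopsis with sections 3.1 and 3.8.1 and Appendix A, so that the exclusion period and the baseline measurement refer to the same visit. There are two ways to do this, and the choice is the sponsor's:

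- Count the period already stated from the Screening/Baseline Visit, as the surgery criterion and section 3.9 already do for their look-backs.
- Keep the Day 0 anchor and take the baseline Schirmer, staining, break-up time and meniscus height tests on Day 0 before instillation.

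In either case, add a confirmation of the criterion to the Day 0 column of Appendix A.

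The cost is a short amendment with no additional visit. Under the first option, a few candidates who recently stopped these drugs would be screened later, by up to 30 days. Under the second, the tear tests move to, or are repeated on, the day of application.

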3.3.3. Inclusion/Exclusion Exceptions

The investigator has the right to exclude a potential participant's enrollment in the study if s/he deems it in the best interest of the participant. Reasons for exclusion on this basis will be recorded.

3.3.4. Discontinuation

A participant may voluntarily discontinue participation in the study at any time without prejudice. The investigator may elect to discontinue a participant for reasons unrelated to the study device (e.g. failure to comply with the study protocol, missed visits, etc.) or for reasons related to the study device (e.g. adverse event). In any event, the reason(s) for discontinuation should be recorded on the CRF. Possible reasons for study discontinuation can include the following:

- AEs necessitating discontinuation from the study
- The participant fails to comply with the study protocol or misses visits
- Participant decision unrelated to AEs
- Investigator decision (specify on CRF)
- Other reason (specify on CRF)

If a participant chooses to discontinue his/her participation or is discontinued by the investigator, the exit CRF should be completed. In case of premature discontinuation from the study, the examiner should perform any testing required to ensure that the participant's ocular health is within normal limits, if the participant agrees.

Participants to be discontinued for AE(s) will be followed until the event is resolved or considered medically stable by the investigator if the participant agrees. If a participant is lost-to-follow-up, the investigator should do his/her best to contact the participant initially by phone, then by letter, and finally by certified mail. Evidence of these contacts should be recorded in the participant's medical chart.

Participants discontinued prior to the initial device application (Day 0) may be replaced and new participants will be assigned new study ID numbers.

3.3.5. Pregnancy

Women of childbearing potential (WOCBP) includes any females who have experienced menarche and who have not undergone successful surgical sterilization (hysterectomy, bilateral tubal ligation or bilateral oophorectomy) or are not postmenopausal with at least 12 months since last menses. WOCBP will be required to use designated methods of birth control during the course of the study. All women who are pregnant, nursing an infant, or planning a pregnancy will be excluded from participation.

During the study, all WOCBP should be instructed to contact the investigator immediately if they suspect they might be pregnant (e.g., missed or late menstrual period). A pregnancy test should be performed and, if the results are positive, the participant should discontinue use of the device and exit from the study. The Exit CRF should be completed and the reason for discontinuing the study should be recorded as pregnancy.

If a participant or investigator suspects that the participant may be pregnant prior to study device application, the study device must be withheld until the results of pregnancy testing are available. If pregnancy is confirmed, the participant must not administer the study device and must not be enrolled in the study or will be withdrawn from the study.

3.4. Expected Duration of Follow-up and of Study

Participants will have the investigational device for up to 42 days. Total elapsed time for study participation will be up to 72 days. The expected duration for the entire study will be up to approximately 3 months.

3.5. Enrollment

Prior to the Screening Visit, potential participants will be provided with an IRB approved informed consent document and have the opportunity to review and ask questions before giving written informed consent. If required, the participant will sign and date the informed consent document in the presence of a witness. The investigator or appropriate staff member will also sign and date the consent form as required. The original will be retained with the participant records and a copy will be provided to the participant.

Once informed consent has been provided, the participant can undergo screening procedures. During the screening examination, participants should be identified only by their initials in the screening and enrollment log. For participants who have no middle name, a dash (-) should be used in place of the middle initial. After the participant has completed the required testing and met eligibility, the participant is considered eligible to participate and will be scheduled to return for Day 0. Once the participant returns for Day 0 and uses the device, they will be considered enrolled in the study and receive a unique identification number.

3.6. Randomization

This is a single-arm, randomized, single-masked study in which one eye will receive the device in the lower canaliculus and the fellow eye will receive a sham injection of saline in the lower canaliculus. The eye which receives the device will be determined by a randomization sequence. The participant will remain masked as to which eye received the device and which eye received the sham.

3.7. Clinical Assessments

The following clinical assessments will be performed for this study:

- Ocular Surface Disease Index (OSDI) questionnaire for each eye individually
- Corrected Distance Visual Acuity
- Tear break-up time
- Tear meniscus height
- Slit-lamp biomicroscopy
- Corneal staining scored using the NEI grid and grading system
- Schirmer test with topical anesthetic

A detailed description of the procedure for each assessment can be found in Appendix B.

3.8. Visit Schedule

This study consists of five visits: Screening, Day 0, Day 3, Day 14 and Day 30. A Schedule of Assessment with a summary of the testing required at each visit can be found in Appendix A.

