Single-Arm, Single-Center, Randomized, Single-Masked Study to Evaluate Restylane-Defyne for Canalicular Occlusion in Participants with Mild to Moderate Dry Eye Disease

Protocol Number: 0918

Protocol Date: July 9, 2018

Version 1.0

Revision History None

Principal Investigator
and Sponsor [name]
The Eye Care Institute
[name]
[name]

Monitor [name]
[name] Consulting, Inc.
[name]
[name]

PROTOCOL 0918 STUDY SYNOPSIS

Protocol Title	Single-Arm, Single-Center, Randomized, Single-Masked Study to Evaluate Restylane-Defyne for Punctal Occlusion in Participants with Mild to Moderate Dry Eye Disease
Study Period	Up to 3 months
Study Population	13 adult participants with mild to moderate dry eye disease
Primary Study Objectives	Safety and effectiveness assessments of Restylane-Defyne for punctal occlusion
Treatments	Participants will receive Restylane-Defyne in the inferior punctum of one eye and a sham injection in the inferior punctum of the fellow eye.
Study Design	Prospective, randomized, single-masked study with unilateral placement of Restylane-Defyne.
Sample Size	Up to 13 participants, with a goal of 10 participants finishing study.
Examination Schedule	Participants will have a Baseline Visit within 30 days prior to the initial device application. Device application will be initiated at Day 0 with follow-up visits at 3 days, 14 days and 42 days. Participants will exit the study after the 6-week visit exam.

Clinical Assessments

Assessments performed will include:

- Ocular Surface Disease Index questionnaire
- Slit-lamp biomicroscopy with grading of corneal staining
- Schirmer test with topical anesthetic
- Tear break-up time
- Tear meniscus height
- Corrected Distance Visual Acuity

Study Endpoints

- **Primary effectiveness endpoint**

Change in Schirmer score from baseline

- **Additional effectiveness endpoints**

Changes in OSDI score, corneal staining score, tear break-up time and tear meniscus height

- **Primary safety endpoint**

Proportion of participants that experience one or more device-related adverse events (e.g., irritation, conjunctival injection, epiphora, subconjunctival hemorrhage, canaliculitis, punctal stenosis, eyelid telangiectasia, eyelid edema, eyelid induration, eyelid erythema).

- **Additional safety assessments**

Corrected distance visual acuity, slit lamp biomicroscopy findings

Inclusion Criteria

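### The final visit, which carries the only post-baseline Schirmer test and the device removal, is set at Day 30 in two places and at Day 42 or 6 weeks in the rest of the protocol

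*Protocol*

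**What the plan says.** Two statements in the visit instructions give Day 30. Section 3.8 reads: "This study consists of five visits: Screening, Day 0, Day 3, Day 14 and Day 30". Section 3.8.4 is headed Day 42 but opens with: "The following procedures are performed at the Day 30 visit".

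Other places give a different day for the same visit:

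- Synopsis, examination schedule: "Device application will be initiated at Day 0 with follow-up visits at 3 days, 14 days and 42 days", and then "Participants will exit the study after the 6-week visit exam".
- Section 3.1: "Participants will be followed for 42 days and will be seen for follow-up exams at 3, 14 and 42 days".
- Section 4.6: the effectiveness comparison between device eye and sham eye runs from baseline to 6 weeks.
- Appendix A: the last column is Day 42 ± 5.
- Section 3.4: "Participants will have the investigational device for up to 42 days", with total participation of up to 72 days.

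The primary endpoint in Section 3.2.1 has no time point: "The primary effectiveness endpoint will be change in Schirmer score from baseline". Section 4.6 is the only place that supplies one. The procedure list in Section 3.8.4 includes the Schirmer test and ends with the instruction "Remove device from inferior canaliculus by irrigation".

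**The concern.** The conflict lies in the operative visit schedule and concerns the visit that produces the effectiveness result. According to Section 3.8 and Appendix A, the Schirmer test, corneal staining, tear break-up time and tear meniscus height are done at screening and at the final visit only. Days 3 and 14 have the OSDI, visual acuity and slit-lamp examination but none of those four measures.

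Staff who follow Section 3.8 and the text of 3.8.4 to the letter would take the sole post-baseline Schirmer reading at Day 30 and remove the device the same day. That reading would not match the 6-week analysis in Section 4.6, and the removal would rule out a later reading with the device in place. The two labels also leave no single standard for judging whether a final visit was on schedule or a deviation, and they leave the time for which the device stays in place ambiguous.

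**Working it through.** **Inputs**

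| Item | Value | Source (Protocol) |
|---|---|---|
| Final visit | Day 30 | 3.8; first sentence of 3.8.4 |
| Final visit | Day 42 | heading of 3.8.4; synopsis; 3.1 |
| Final visit with window | Day 42 ± 5 | Appendix A |
| Analysis time point | 6 weeks | 4.6 |
| Screening period | up to 30 days before Day 0 | 3.8.1; Appendix A |
| Time with device | up to 42 days | 3.4 |
| Total participation | up to 72 days | 3.4 |

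**The plan's own figure.** Longest screening period plus final visit day: 30 + 42 = 72 days. This reproduces the total in Section 3.4. With a Day 30 final visit the longest participation is 30 + 30 = 60 days.

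**Weeks against days.** 6 × 7 = 42 days, so Section 4.6 agrees with the Day 42 label and not with Day 30.

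**Size of the gap.** 42 − 30 = 12 days, and 12/42 = 28.6% of the 42-day period.

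**Can the window absorb it?** Appendix A runs from 42 − 5 = Day 37 to 42 + 5 = Day 47. Day 30 is 37 − 30 = 7 days before it opens. Section 3.8 gives no tolerance around Day 30. If the same ± 5 days is assumed there, the visit could fall between Day 25 and Day 35, and this range still does not meet Day 37 to 47.

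**Can another visit supply the value?** No. Neither the lists in Section 3.8 nor Appendix A schedule a Schirmer test on Day 0, Day 3 or Day 14. Removal is scheduled at the final visit, and participants leave the study after it.

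**Side check on Section 3.4.** At the end of the Appendix A window a participant would have had the device for 47 days, against the stated limit of 42. Total participation would reach 30 + 47 = 77 days, against the stated 72.

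**The case against.** The strongest reply is that this is an evident drafting slip. The Day 42 heading stands directly above one of the two Day 30 sentences, and the other sends the reader to Appendix A, which gives Day 42 and the only visit window. There is one centre, and the principal investigator is also the sponsor, so sites cannot read the text differently. The study is a pilot of up to 13 participants with no hypothesis and no sample size calculation, so no power or error rate depends on the visit day. The analysis time point in Section 4.6 is stated once and not contradicted, so the missing time point in Section 3.2.1 is not a separate defect.

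Much of this stands, and it lowers the chance that anyone would be seen at Day 30. It is also fair that the limits in Section 3.4 are upper limits. A Day 30 visit satisfies both of them, so 60 against 72 days is not in itself a contradiction and shows only that 72 was built from 42. Section 3.4 can likewise be read as nominal, without visit windows, which makes the 47-day and 77-day figures a minor drafting matter.

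The reply does not remove the conflict. The protocol is version 1.0 with no revision history, so neither label is left over from superseded text. The Day 30 label appears twice, both times in the section that tells staff what to do and when. An endpoint measured only once after baseline should not depend on the reader's inference.

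**Conclusion.** The protocol is wrong as written. Section 3.8 and the first sentence of 3.8.4 contradict the heading of 3.8.4, the synopsis, Section 3.1, Section 4.6 and Appendix A on the day of the final visit. The gap is 12 days, and 7 days lie between Day 30 and the opening of the Appendix A window. Section 3.4 supports the 42-day reading only indirectly.

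The conflict is about the day of the measuring visit, not between two defined endpoints, since no 30-day analysis is described anywhere. The loss of a usable 6-week value arises only for a participant actually seen at Day 30, and the documents give no basis for saying how many that would be, if any. With a goal of 10 completers, one such participant would be 1/10 = 10% of the primary endpoint data. This conclusion rests on the text alone and on no assumption about effect size or variability. It does not say which day is right.

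**What to change.** Correct this before enrolment:

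- Reconcile Section 3.8 and the opening sentence of 3.8.4 with the heading of 3.8.4, the synopsis, Section 3.1, Section 4.6 and Appendix A, so that all name one final-visit day and one window.
- Have Section 4.6 refer to that visit by name. Repeating the time point in Section 3.2.1 would help but is not essential.
- As a minor item, make the device-time and participation limits in Section 3.4 consistent with the visit window, or say that they exclude it.

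The choice of day and limits is for the sponsor and investigator. The cost is protocol wording: no added visit, procedure or participant. Whether any stated duration changes depends on how the passages are reconciled.
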